### 11.4.2 Loss of capacity

As the maximum time during which a participant will be enrolled in this study is 1 month, it is unlikely they will lose capacity because of dementia. For this reason we will not routinely assess for this. However, if someone loses capacity and we become aware of this, we will respect their consent and include the data we have already collected from them in our analyses. However, we will exclude them from any further testing as we have defined capability to consent as an inclusion criteria for this study.

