#### 4.2 Inclusion Criteria

### For Sub-Study 1

- 1. Age > 50
- 2. All participants must express that they are willing to take part in this study and adhere to the study procedures
- 3. Full capacity to consent to involvement
- 4. Clinical diagnosis of MCI due to AD[52] or mild AD[51] according to standardised criteria

(NB people with a mixed AD/Vascular dementia diagnosis are eligible for inclusion)

### For Sub-Study 2

- 1. All participants undergoing CSF testing clinically including CSF biomarkers of AD.
- 2. All participants must express that they are willing to take part in this study and adhere to the study procedures.
- 3. Full capacity to consent to involvement

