#### Follow-up checks of medical records

Medical records from participants in both substudies will be checked again at 2 years and at 5 years after involvement in the study. This will only include available records from those participants in the pre-clinical/MCI phase at time of participation in the study. In both substudies, the date will be measured from the date of the last participant's venepuncture. This follow-up data will be extracted to identify whether the pre-clinical / MCI diagnosis has changed to a dementia diagnosis.

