#### 9.5 Data Loss

The technology used in the study will be set up for each participant according to a rigorous protocol agreed by the research team, and participants are provided with written and verbal information on study activities to ensure adherence to protocol. However due to the remote and technology-focused nature of the study, it is possible for data to be lost or not collected due to technological issues (e.g., battery failures).

If a significant portion of data is missing on a given task, participants may be asked if they are willing to repeat an EEG night or blood test if appropriate within the 3 month study period. The participant can decline repeating any measures without this affecting their participation in the study. Similarly, if appropriate in the opinion of the Chief Investigator, participants may be asked to complete study activities outside of their main study period if study protocol has changed (and participants will be reconsented as appropriate).

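### Section 11.4.2 waives routine re-assessment of capacity because enrolment lasts at most 1 month, but section 9.5 allows repeat EEG nights and blood tests within a 3-month study period and states no capacity recheck for them

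*Protocol*

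**What the plan says.** Section 4.2 lists, for both sub-studies, "Full capacity to consent to involvement" as an inclusion criterion. Section 5.3 describes how the researcher assesses capacity while going through the information sheet at consent.

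Section 11.4.2 deals with what happens afterwards. Its premise, which is about loss through dementia, is "As the maximum time during which a participant will be enrolled in this study is 1 month, it is unlikely they will lose capacity". The consequence follows at once: "For this reason we will not routinely assess for this". If the team does become aware that someone has lost capacity, data already collected are kept, and "we will exclude them from any further testing as we have defined capability to consent as an inclusion criteria for this study".

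Section 9.5 covers lost or missing data. Where a significant part is missing, "participants may be asked if they are willing to repeat an EEG night or blood test if appropriate within the 3 month study period". They may decline. The section then adds a separate provision: if the protocol has changed and the Chief Investigator thinks it appropriate, "participants may be asked to complete study activities outside of their main study period", with renewed consent as appropriate.

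**The concern.** The 1-month figure is the only reason that section 11.4.2 gives for having no routine check, so it matters whether the figure is right. If procedures can take place well after one month, the protocol has no stated ground for assuming that the capacity established at consent still holds when a repeat EEG night or venepuncture is carried out.

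Sub-Study 1 enrols people with mild cognitive impairment due to Alzheimer's disease or mild Alzheimer's disease. The protocol itself treats capacity as a condition both of entry and of further testing. A site following the text could carry out a repeat procedure on someone who no longer meets that condition, because the rule acts only once the loss is already known. What is at stake is participant protection and a rule that can be applied consistently. It is not the precision of an estimate.

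**Working it through.** This is a comparison of stated durations. No sample-size or power figure is involved.

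**Inputs**

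| Item | Stated value | Protocol section |
|---|---|---|
| Maximum enrolment, used to justify the waiver | 1 month | 11.4.2 |
| Study period in which EEG nights or blood tests may be repeated | 3 months | 9.5 |
| Activities outside the main study period | allowed after a protocol change; no upper time limit; renewed consent as appropriate | 9.5 |
| Core Sub-Study 1 schedule | eligibility call, initial visit, 3 EEG nights, questionnaire within 1 week of testing | 8.2 |

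The timeline figure for section 7.1 cannot be read in the text reviewed. A fragment beside it also gives a limit of 3 months. That agrees with 9.5, but the point does not depend on it.

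**Step 1: can the 1-month figure be reproduced?** The core schedule in 8.2 could be completed in a month. Section 11.4.2, however, states a maximum, and 9.5 permits procedures beyond it. One month cannot be reproduced as a maximum.

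**Step 2: size of the gap.** Assume that both periods start from the same point, such as consent; 9.5 does not say when its 3 months begin.

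- Ratio: 3 months / 1 month = 3.
- Time not covered by the stated reason: 3 − 1 = 2 months.

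**Step 3: what protects a participant in those 2 months?**

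- Repeat EEG night or blood test within the 3 months: the participant is asked and may decline. No capacity recheck is stated.
- Activity outside the main study period after a protocol change: renewed consent as appropriate. Under 5.3, taking consent includes assessing capacity.
- Loss of capacity that becomes known: no further testing, under 11.4.2.

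The uncovered case is the first: a repeat inside the 3-month period in someone whose loss of capacity has not come to the team's notice.

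**The case against.** The strongest reply is that the gap is narrow. Section 11.4.2 waives only routine assessment and keeps a rule for known loss of capacity. A researcher is in the home on every EEG night (6.4.1) and would probably notice a marked change. Repeats are voluntary. In Sub-Study 2 blood is drawn once, with the clinical lumbar puncture (8.2), and written consent is confirmed at that appointment (5.1), so the problem hardly arises there. The protocol's expectation that dementia will rarely remove capacity over a short period may also be true at 3 months. All of this stands, and it limits the size of the point. It does not repair the reason as written, and it does not supply a recheck for repeats.

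Three stronger readings are tempting, but the documents do not support them.

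- A reader might infer that capacity is never looked at again. The provision for activities outside the main study period carries renewed consent, and the rule for known loss remains.
- A reader might set the 1 month against the long-term follow-up: "Medical records from participants in both substudies will be checked again at 2 years and at 5 years after involvement in the study". These are checks of records with no contact or testing. The protocol places them after involvement, and section 15 separates them from the main study. They contradict 1 month only if enrolment is taken to include passive record review.
- A reader might infer that people who progress to dementia would drop selectively out of the follow-up outcome. Section 11.4.2 stops further testing, not extraction from records, and does not say that only existing data are kept. No study contact is scheduled between the active phase and the 2-year check, so there is no planned route by which the team would learn of the loss and then skip the check. The documents give no figure from which a bias could be calculated.

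**Conclusion.** The point holds in a limited form. The stated reason for not routinely re-assessing capacity is contradicted by the protocol's own study period: 1 month against 3. That leaves up to 2 months in which an EEG night or blood test may be repeated without a stated recheck, although full capacity is required for entry and its loss bars further testing. The 2-month figure assumes a common starting point for the two periods.

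What fails is the reason given, not necessarily the expectation behind it: nothing in the protocol shows that loss of capacity is likely by 3 months. No effect on the feasibility, accuracy or follow-up estimates is claimed. The inconsistency should still be corrected, because a participant-protection rule rests expressly on the figure and the correction is cheap.

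**What to change.** 1. Reconcile the duration across 11.4.2, 9.5 and 7.1, and say when the period starts.
2. Remove the 1-month rationale from 11.4.2 or correct it to the reconciled duration.
3. Add that, before any repeat procedure, the researcher attending it briefly confirms and records continuing capacity and willingness.
4. Optionally, add a sentence to 11.4.2 that exclusion from further testing does not end the 2- and 5-year record checks to which the participant consented, and check that the consent form says the same. The consent pages were not available here, so whether they already do so is unknown.

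The cost is protocol wording and one entry on the record form at attendances that take place anyway, with no extra visits or staff. The small downside is that a few repeats may not go ahead, leaving those nights or samples missing.

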#### 11.5 Participant Burden

Overall, this study has a relatively low burden on participants, with the focus being obtaining data (sleep patterns and memory tests) that reflects everyday life for the participants. The technology planned to measure these patterns is specifically designed to be non-invasive, with the exception of a one-off blood test for some participants.

Screening and baseline consultations will be conducted face to face or remotely permitting us to flexibly mitigate COVID-19 or future pandemics.

All visits to the patient's home should last no longer than two hours. All equipment and study materials will be collected from the participants when data collection has ended.

The cognitive tests will require mental effort on the part of participants. Participants are free to stop the test at any time and this will be re-iterated prior to the start of the test.

The sleep diary will only need to be completed each morning. This should take no more than 2 minutes to complete each day.

SleepAD Protocol v6.0 6th September 2024

Venepuncture causes a brief stinging sensation that is usually well tolerated and occasionally triggers syncope in the minute or two afterwards, or causes a bruise later on. Participants will be seated during venepuncture and will be observed and offered suitable refreshments afterwards in case of any immediate syncope.

We will not be able to meaningfully feedback the blood biomarker or CSF/ plasma orexin results as we are using a research only laboratory without validated normal ranges which we will extrapolate from the clinic laboratory at UCL. Therefore we will not be able to disclose AD risk on the basis of blood biomarkers – thus avoiding potential participant burden to decide if they would like to know.

Similarly, we will not be able to meaningfully feedback the results of the *APOE* genotyping. The results will be for research purposes only and not performed as a clinical test. We are not undertaking the genetic testing in a validated clinical laboratory, and NICE guidelines specifically advise against disclosing the outcome. As we will not be disclosing AD risk on the basis of genotyping this avoids adding potential participant burden to decide if they would like to know.

If participants agree to an extra <5ml of CSF being taken for secondary validation of blood results, there is a low chance we may worsen a post-lumbar puncture headache. This can be mitigated in most cases by drinking fluids and lying flat and we will reinforce the advice already given to people having lumbar puncture to reduce the risk of post-LP headache.

#### 12 ADVERSE EVENTS

This observational study does not involve administration of any medicinal product and utilises non-invasive passive monitoring devices only.

Due to the low risk nature of the project, and the comparatively long length of follow-up, only adverse events assessed as related to study procedures will be recorded. Participants will be asked at each contact if they have experienced any adverse events. Adverse events considered related to a protocol procedure will be recorded at site and entered into an eCRF. Serious adverse events will be reported to the Sponsor. Adverse event reporting will follow the research safety reporting standard operating procedure of University Hospitals Bristol and Weston NHS Trust who manage safety reporting on behalf of the Sponsor.

Adverse events that are judged to be possibly, probably, or definitely related to the EEG and meet one of the criteria for a serious adverse event will be reported to the Sponsor within 24 hours of the research team becoming aware of the event.

Serious adverse events are considered if any of the following criteria apply to an adverse event:

- Results in participant's death
- Is life threatening
- Results in hospitalisation or prolongs existing hospitalisation
- Results in a persistent or significant disability or incapacity
- Consists of a congenital anomaly or birth defect

SleepAD Protocol v6.0 6th September 2024

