#### 5 PARTICIPANT SELECTION AND ENROLMENT

### 5.1 Pre-screening potential participants

### For Sub-Study 1

All prospective participants will first be contacted by telephone (or face to face if consultation planned) by a member of the clinical team to establish whether they are potentially interested in participating, and if so, details will be passed to a member of the research team.

A member of the research team will then make contact by phone to provide an outline of the study and will ask about their general health. This is in order to rule out participants who have medical diagnoses or problems that may prevent them from taking part in this study, such as a severe medical co-morbidity interfering with sleep. Another goal of the pre-screening phone call is to schedule the first screening consultation. We will give the potential participant as much time as they need to decide whether they wish to undergo the first screening consultation.

If the prospective participant does not already possess a copy of the Patient Information Sheet (PIS), this will be sent by post or electronically. Prospective participants with a carer are invited to bring this person along with them for the screening consultation.

#### For Sub-Study 2

Clinicians will consider eligibility for the study at the point of booking patients in for a routine lumbar puncture in the Brain Centre clinic, and if the prospective participant is interested they will be signposted to the research team. A member of the research team will then make contact by phone to discuss the study, and if appropriate to gain verbal consent to participate.

SleepAD Protocol v6.0 6th September 2024

For participants with speech or communication difficulties, a face-to-face appointment will be offered instead of a phone call.

During the subsequent lumbar puncture appointment, consent will be confirmed in writing by a GCP trained member of the team.

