### 8.2 Frequency of Data Collection

### For substudy 1

Data will be collected during a one-off eligibility telephone conversation, an initial visit, over 3 nights of sleep EEG and then with acceptability questionnaire within 1 week of overnight testing.

Baseline data collected during the eligibility telephone conversation and initial visit will be entered by researchers into paper case report forms and then into REDCAP (electronic data capture system) or directly into REDCap. Data collected during the Study Assessment Period will comprise raw electronic data from measurement devices which will be downloaded onto secure computers at the end of the assessment period and memory test results that will be uploaded onto REDCap after testing.

#### For Substudy 2

Demographic and clinical data will be extracted from electronic medical records. Venepuncture will occur only once at the same time as clinical LP.

SleepAD Protocol v6.0 6th September 2024

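### Adverse events are asked about only at contacts, and people in Sub-study 2 alone have none scheduled after the lumbar puncture, so headache worsened by the research CSF is not systematically captured

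*Protocol*

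**What the plan says.** Section 12 sets out how adverse events are found and which are kept. They are found by asking: "Participants will be asked at each contact if they have experienced any adverse events". They are kept selectively: "only adverse events assessed as related to study procedures will be recorded". Related events go into the eCRF, and reporting follows a safety procedure that is not part of the document.

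Section 11.5 names the risk of the optional CSF sample in Sub-study 2: "there is a low chance we may worsen a post-lumbar puncture headache".

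For the Sub-study 2 schedule, section 5.1 has the research team telephone the patient before the procedure (or see the patient in person if communication is difficult), and then: "During the subsequent lumbar puncture appointment, consent will be confirmed in writing by a GCP trained member of the team". Section 5.2 states that there is no screening visit. Section 8.2 adds "Venepuncture will occur only once at the same time as clinical LP" and "Demographic and clinical data will be extracted from electronic medical records". The later follow-up in section 8.2 is a check of records: "Medical records from participants in both substudies will be checked again at 2 years and at 5 years after involvement in the study". It covers only people who were pre-clinical or had MCI at entry, and looks only for a change to a dementia diagnosis.

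**The concern.** The safety question is tied to contacts, and in Sub-study 2 the last scheduled contact is the procedure itself. The one risk that the protocol ascribes to the research CSF can show itself after that appointment ends. A site following the protocol exactly would ask its last adverse-event question too early to hear about it.

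The relatedness filter adds a second difficulty. The extra CSF is drawn during a lumbar puncture done for clinical reasons, so every headache has a competing cause outside the study. Section 12 does not say how to classify such a headache.

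At stake is the safety record of a research procedure. A count of zero or near zero would partly reflect when the question was asked, and could not be used to check the protocol's own description of the risk as low.

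**Working it through.** There is no figure in the plan to reproduce. The check is to list every contact for a person in Sub-study 2 alone and compare it with the adverse-event rule.

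- **Before the puncture:** a call, or a face-to-face appointment for those with communication difficulties (section 5.1). No screening visit (section 5.2).
- **At the puncture:** written consent, blood, and optional extra CSF of less than 5 ml (sections 5.1 and 6.3). An adverse-event question can be asked here.
- **After the puncture:** no scheduled contact. Demographic and clinical data come from records (section 8.2). The acceptability questionnaire within 1 week of the last session is listed under Sub-study 1 only (section 6.3).
- **At 2 and 5 years:** a records check limited by group and purpose (section 8.2). Nobody is contacted and no safety data are sought.

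Scheduled contacts after the procedure: 0.

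Three unscheduled or partial routes remain. Section 4.1 expects many Sub-study 2 patients to join Sub-study 1 as well, which brings EEG evenings and the questionnaire, but these are not timed to the puncture. Section 6.3 allows a separate MoCA visit or video call in a very rare case, not stated to follow the puncture. Section 9.5 allows a request to repeat a blood test if data are missing. None is a planned safety contact.

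Section 12 can also be set against the rest of the protocol. It describes the study as using only passive, non-invasive monitoring devices, and its 24-hour reporting rule is written for events related to the EEG. Section 6.3 makes venepuncture and the extra CSF study procedures. Section 12 partly justifies restricted recording by the length of follow-up, but that follow-up is the records check above.

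The precision of a comparison by extra CSF (yes/no) can be gauged under assumptions. Take all 100 participants split 50/50, with the same headache rate p in each group. Neither figure is in the protocol. The 95% half-width for the difference is 1.96 × √(2p(1−p)/50):

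- p = 5%: 1.96 × √0.0019 = 8.5 percentage points
- p = 10%: 1.96 × √0.0036 = 11.8 percentage points
- p = 20%: 1.96 × √0.0064 = 15.7 percentage points

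Such a table would be descriptive and could not settle a small effect of the extra volume.

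**The case against.** The strongest reply is that section 12 requires a question at each contact but does not confine recording to events found that way. A headache that the participant reports unprompted, or that reaches the clinic that did the puncture, can be recorded, and the unseen safety procedure may say more. That stands. A reader might infer that delayed headache cannot be captured at all; the text supports only that capture is not systematic.

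Nor does any section say that a headache with an uncertain cause is to be judged unrelated, though a reader might expect a site to do so. Section 11.5 itself links worsening to the extra CSF, and the only causality scale shown, the one for the EEG, includes possibly related events. What stands of the concern is that no rule is given for this case.

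The protocol also mentions that venepuncture "occasionally triggers syncope in the minute or two afterwards, or causes a bruise later on", and a reader might count the later bruise as a second missed harm of Sub-study 2. The text does not support that. In Sub-study 2 the blood is drawn alongside the clinical sample, so except in very rare situations there is no added needle-stick. A separate research venepuncture is described mainly for Sub-study 1, which has later contacts and a questionnaire item on blood testing.

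Finally, CSF safety is neither an objective nor a planned analysis, and restricting records to related events is a deliberate choice for a low-risk observational study. This limits the weight of the point but does not supply the missing contact.

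**Conclusion.** The point holds in a limited form. For people in Sub-study 2 alone, the only stated active route for adverse events closes at the procedure visit, so worsened post-puncture headache is not systematically captured. Whether a headache that does come to light is recorded depends on individual judgement.

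The size is zero scheduled post-procedure contacts for up to 100 participants, fewer to the extent that they also join Sub-study 1. The number exposed to the extra CSF cannot be stated, because the sample is optional and no uptake is given. A reader might want an expected number of missed events or an upper confidence limit based on 100 people. Neither would measure harm from the extra CSF: a general rate of headache after lumbar puncture mostly reflects the clinical procedure, and 100 is not the exposed number.

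The conclusion rests on the schedule in the protocol being complete and on the unseen safety procedure not adding a contact. It is worth acting on because the remedy is cheap, but it does not affect the study's primary objectives.

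**What to change.** In sections 8.2 and 12:

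1. Add one brief adverse-event contact by phone or e-mail within about 1 week of the lumbar puncture for Sub-study 2 participants, or at least for those who give extra CSF. If the yes/no table below is wanted, everyone must be asked.
2. Record any post-puncture headache in the eCRF regardless of judged relatedness, so that the count does not depend on an attribution that cannot be made reliably in one patient.
3. Report headache descriptively by extra CSF taken (yes/no), stating that the groups are self-selected and the comparison imprecise.
4. Reconcile section 12's description of the study procedures, and its EEG-only 24-hour rule, with venepuncture and extra CSF being study procedures.

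The cost is one short call or message per participant by the existing team, one eCRF item and one table. The headache count will include events due to the clinical puncture, and the report should say so.
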